Vacc = Vaccination; **PC** = Phone Contact; **AEs** = Adverse Events; **CMI** = Cell- Mediated Immunity; **SAEs** = Serious Adverse Events; **pIMDs** = potential Immune-Mediated Diseases;

HZ = Herpes Zoster; **AESI** = Adverse Events of Special Interest; **RT** = Renal Transplant; **ZBPI** = Zoster Brief Pain Inventory.

^a Before vaccine administration.

^b A Phone contact 1 (PC1) will occur about 35 days before Visit 3 (Month 24) to remind female subjects of childbearing potential to use adequate contraception.

^c Visit 3 is the day of the first revaccination. Pre-revaccination and post-revaccination activities at Visit 3 are part of Epoch 001 and Epoch 002, respectively.

^c Visit 4 is the day of the second revaccination that will be administered 1 to 2 months after the first revaccination. The subsequent visits (Visit 5, Visit 6 and Visit 7) will occur within 1, 12 and 24 months after the second revaccination, respectively.

^d An *ad-hoc* HZ Visit will be planned in case of suspected HZ and will be scheduled preferably within 3 calendar days from appearance of HZ symptom(s).

^e Study activity to be performed at the next scheduled visit, if this has not been performed during the *ad-hoc* HZ visit.

^f A second written informed consent will only be obtained prior to performance of any revaccination procedures, if required by local regulatory authorities or Institutional Review Boards (IRB)/Independent Ethics Committees (IEC).

^g Blood sample *is substituted for urine sample* for pregnancy **testing as** required by country, local or ethics committee regulations. **Pregnancy testing should be completed, and results reviewed prior to revaccination.**

^h For non-revaccinated subjects (see [Glossary of terms for the definition and Section 8.1, for details](#)), Visit 4 and 5 will not occur.

For non-revaccinated subjects, see Section 8.1.

Note:

In times of special circumstances, refer to Section 8.1.16 for study procedures.

(Amended: 15 June 2020)

CONFIDENTIAL

212340 (ZOSTER-073 EXT:041 Y4-10)

Protocol Amendment 1 Final

Whenever possible, the investigator should arrange study visits within the intervals described in [Table 4](#).

Table 4 **Intervals between study visits**

Interval	Optimal length of interval ^a	Allowed interval (days) ^b
Visit 1 (Day 1) → Visit 2 (Month 12)	12 months (360 days)	330 - 415
Visit 1 (Day 1) → Visit 3 (Month 24)	24 months (720 days)	690 - 775
PC 1 (Day 695) → Visit 3 (Month 24)	35 days	31 - 40

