7.4. Handling, storage and replacement of study vaccine

The study vaccine has been developed and manufactured by GSK.

The Quality Control Standards and Requirements for the study vaccine are described in separate Quality Assurance documents (e.g. release protocols, certificate of analysis) and the required approvals have been obtained.

The vaccine is labelled and packed according to applicable regulatory requirements.

For information on dosage and administration of the study vaccine, refer to [Table 7](#). The study vaccine will be administered on Visit 3 (Month 24) and Visit 4 (Month 25).

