8.1.8. Pre-revaccination body temperature

The oral (preferred route) body temperature of each subject needs to be measured prior to any study vaccine administration and recorded in the eCRF. If the subject has fever [fever is defined as temperature $\geq 38.0^{\circ}\text{C}$ (100.4°F) regardless of route of measurement] on the day of vaccination, the revaccination visit will be rescheduled within the allowed interval for this visit (see [Table 4](#)). ***Pre-revaccination temperature measurements should not be performed for non-revaccinated subjects.*** **(Amended: 15 June 2020)**

CONFIDENTIAL212340 (ZOSTER-073 EXT:041 Y4-10)
Protocol Amendment 1 Final**8.1.9. Record serum creatinine measures**

As the detection of kidney allograft function is paramount to the management of allograft health and prevention of allograft rejection, transplant centers have established vigorous routine clinical surveillance protocols for the monitoring of the allograft. This study will rely on these per site “surveillance protocols” and will not mandate the type or timing of tests to participating study sites.

To follow allograft function, the available serum creatinine measurements, obtained per the site’s “surveillance protocol” or for “clinical indication” (locally available), will be recorded in the eCRF.

Record ALL serum creatinine obtained:

- **For Allograft rejection**

- For 2 months prior to a biopsy-proven allograft rejection, as event baseline. If not 2 or more measurements in 2 months, then go back to 3 or 4 months prior to biopsy to have a minimum of 2 measurements.
- From onset of allograft rejection through resolution.
- For 2 months after resolution of the biopsy-proven rejection and the cessation of therapeutic immunosuppressive therapy, so that 2 or more additional post-rejection measurements are recorded.

Post-allograft rejection serum creatinine measurements will be evaluated in comparison to the subject’s baseline pre-allograft rejection measurements.

- **For revaccination**

- For 3 months prior to first revaccination, Visit 3 (Month 24), as pre-vaccination baseline. If not 3 or more measurements in 3 months, then go back to 4 or 5 months prior to revaccination to have a minimum of 3 measurements.
- From Visit 3 (Month 24) through Visit 5 (Month 26).
- For 3 months after last revaccination, Visit 5 (Month 26), so that 3 or more additional post-revaccination measurements are recorded.

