- *If despite best efforts, it is not possible to administer the second dose of study vaccine as defined in the protocol (see Table 4), a maximum dose interval of up to 6 months after the first revaccination dose may be used. If the maximum dose interval length is exceeded, then vaccination should be discontinued.*

Impact on the per protocol set (PPS) for immunogenicity will be determined on a case by case basis.

CONFIDENTIAL212340 (ZOSTER-073 EXT:041 Y4-10)
Protocol Amendment 1 Final**Table 8** *Intervals between study visits during special circumstances*
(Amended: 15 June 2020)

Visits	At the discretion of Sponsor, during special circumstances		Notes
	Visit(s) may be delayed	Allowed interval (days)	
Visit 2	Up to 6 months		The length of the allowed interval (85 days) remains, but the start of the interval may be moved by up to 6 months (starting no later than 18 months post-Visit 1), e.g. to avoid potential seasonal recurrence of COVID-19
PC 1		30 – 40 days before Visit 3	
Visit 3	Up to 6 months		The length of the allowed interval (85 days) remains, but the start of the interval may be moved by up to 6 months (starting no later than 30 months post-Visit 1), e.g. to avoid potential seasonal recurrence of COVID-19
Visit 4		30 – 182 post-Visit 3	Optimally 30 - 60 days after Visit 3 (Table 4)
Visit 5		30 – 90 post-Visit 4	Optimally 30 – 48 days after Visit 4 (Table 4)
Visit 6*		330 – 445 post-Visit 4	
Visit 7*		690 – 805 post-Visit 4	
Visit 7 may be:
 
 Scheduled earlier to make up for delays incurred during times of special circumstance, in order to maintain planned duration of the study. Delayed or cancelled if special circumstances preclude the original planned visit.

*Note: Investigator should prioritize conducting the visit as close to the optimal window as possible.*** The allowed interval for Visits 6 and 7 should be the same for both the re-vaccinated and non-revaccinated subjects.*

(Amended: 15 June 2020)

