	
 – Occurrence, intensity of unsolicited AEs during 30 days after each revaccination (i.e., the day of revaccination and 29 subsequent days) and causal relationship to revaccination by investigator assessment. • SAEs 
 – Occurrence of SAEs (including fatal SAEs) from Dose 1 of revaccination (Month 24) until 12 months post-last revaccination dose (Month 37). – Occurrence of related-SAEs (including related-fatal SAEs) as per investigator assessment from Dose 1 of revaccination (Month 24) up to study end (Month 49). • AESIs 
 – Occurrence of all biopsy-proven allograft rejections from Dose 1 of revaccination (Month 24) up to study end (Month 49) and causal relationship to revaccination by investigator assessment. – Occurrence of pIMDs from Dose 1 of revaccination (Month 24) up to 12 months post-last revaccination dose (Month 37) and causal relationship by investigator assessment. • HZ episodes 
 – Occurrence of confirmed HZ cases from Dose 1 of revaccination (Month 24) up to study end (Month 49). • Allograft function following revaccination 
 – Occurrence of allograft dysfunction through assessment of all clinically obtained serum creatinine measures from 3 months before the first revaccination dose until 3 months after the last revaccination dose. • Allograft function for episode(s) of allograft rejection 
 – Occurrence of allograft dysfunction through assessment of all clinically obtained serum creatinine measures from 2 months prior to an episode of biopsy-proven rejection and up to 2 months after rejection resolution and cessation of therapeutic or immunosuppressive therapy. • Allograft function for episode(s) of HZ 
 – Occurrence of allograft dysfunction through assessment of all clinically obtained serum creatinine measures from 2 months prior to an episode of HZ and up to 2 months after HZ resolution.

Objectives	Endpoints
CCI	Tertiary

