**Visit 5 (study Month 26), Visit 6 (study Month 37) and Visit 7 (study Month 49) will occur 1, 12 and 24 months after the second revaccination, respectively.

\$Phone contact will occur about 35 days before Visit 3 (study Month 24) to remind female subjects of childbearing potential to use adequate contraception.

Overview of Study Design Key Features

Design Features	
• Type of study: extension of other protocol(s); ZOSTER-041 for the analysis of long-term immunogenicity and safety.• Experimental design: Phase IIIB, open-label, uncontrolled, multi-centric, single group study.• Duration of the study: The study duration per subject will be approximately 49 months.
– Epoch 001: LTFU phase starting at Visit 1 (Day 1) and ending at Visit 3 (study Month 24)– Epoch 002: Revaccination phase starting at Visit 3 (study Month 24) and ending at Visit 7 (study Month 49)• Primary completion Date (PCD): Visit 5 (study Month 26). The date that the final subject was examined or received an intervention for the purpose of final collection of data for all primary outcomes, whether the clinical trial was concluded according to the pre-specified protocol or was terminated• End of Study (EoS): Last testing results released of samples collected up to Visit 7 (study Month 49).• Study group:
------------------------	---

Table 1 Study group, treatment, and epochs in the study

Study groups*	Target Number of subjects	Actual Number of subjects	Age (Min-Max)**	Treatment name	Epochs	
					From ZOSTER-041 primary study	Epoch 001 (open)
HZ/su	86	68	20 years - 82 years	HZ/su	•	•

HZ/su = Herpes Zoster subunit vaccine.

*HZ/su Group name for subjects who were vaccinated with 2 doses of HZ/su in study ZOSTER 041.

**Age at the first vaccination in study ZOSTER-041.

- **Control:** uncontrolled.
- **Revaccination schedule:** Subjects will receive two additional doses of the HZ/su vaccine, at Visit 3 (study Month 24) and at Visit 4 (study Month 25) in the revaccination phase.
- **Treatment allocation:** All eligible subjects will be enrolled into HZ/su group.
- **Blinding:** Open-label.
- **Sampling schedule:**
 - Blood samples to assess humoral immunogenicity will be collected from all subjects at Visit 1 (Day 1), Visit 2 (study Month 12), Visit 3 (study Month 24), Visit 4 (study Month 25)*, Visit 5 (study Month 26)*, Visit 6 (study Month 37) and Visit 7 (study Month 49).

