6.2.3. Multiple measurements at One Analysis Time Point

Baseline and post-baseline serum creatinine measures are computed as follows:

- For Allograft rejection:
 - The average of measurements 2 months prior to a biopsy-proven allograft rejection will be used as event baseline. If there are not 2 or more measurements in 2 months, then go back to 3 or 4 months prior to biopsy to have a minimum of 2 measurements.
 - The maximum of measurements taken up to 2 months after resolution of the biopsy-proven rejection, so that 2 or more additional post-rejection measurements are recorded, will be used to determine declining allograft function compared to baseline pre-allograft rejection measurements.
- For revaccination:
 - The average of measurements taken 3 months prior to first revaccination, Visit 3 (Month 24), will be used as pre-vaccination baseline. If there are not 3 or more measurements in 3 months, then go back to 4 or 5 months prior to revaccination to have a minimum of 3 measurements.
 - The maximum of measurements taken up to 3 months after last revaccination, Visit 5 (Month 26), so that 3 or more additional post-revaccination measurements are recorded, will be used to determine declining allograft function compared to pre-revaccination
- For episode of HZ cases:
 - The average of measurements taken 2 months prior to a HZ episode, will be used as event baseline. If there are not 2 or more measurements in 2 months, then go back to 3 or 4 months prior to HZ episode to have a minimum of 2 measurements.
 - The maximum of measurements taken up to 2 months after HZ episode rash resolution, so that 2 or more post-HZ resolution measurements are recorded, will be used to determine declining allograft function compared to pre-HZ episode.
- For non-revaccinated subjects:

- The mean of the available values before primary vaccination is used as baseline value.
- The maximum of the available values after Visit 3 Month 24 up to study end is used for calculating fold increase

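### SAP 6.2.3 anchors the post-revaccination creatinine window on Visit 5, where no dose is given; the endpoint runs to 3 months after the last dose, which is at Visit 4

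*SAP*

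**What the plan says.** The endpoint, worded alike in protocol Table 5 and SAP 1.1, is allograft dysfunction judged on all clinically obtained serum creatinine values "from 3 months before the first revaccination dose until 3 months after the last revaccination dose".

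The derivation is in SAP 6.2.3. Baseline is the mean of the values in the 3 months before the first revaccination, correctly labelled Visit 3 (Month 24). The post-baseline value is "The maximum of measurements taken up to 3 months after last revaccination, Visit 5 (Month 26". SAP 4.3.2.2 calls a fold increase of 1.2 or more dysfunction, and SAP 4.5.3.1 also tabulates 1.5, 1.75 and 2-fold.

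The same label stands in the collection rule, protocol 8.1.9. Creatinine is recorded from Visit 3 through Visit 5, and then "For 3 months after last revaccination, Visit 5 (Month 26), so that 3 or more additional post-revaccination measurements are recorded".

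The dosing text is consistent throughout. Protocol 7.4: "The study vaccine will be administered on Visit 3 (Month 24) and Visit 4 (Month 25". SAP 1.2 places the two doses "at Visit 3 (study Month 24) and at Visit 4 (study Month 25) in the revaccination phase". The Schedule of Activities footnote says "Visit 4 is the day of the second revaccination that will be administered 1 to 2 months after the first revaccination". Visit 5 is the first of three visits that, in the SAP 1.2 design overview, "will occur 1, 12 and 24 months after the second revaccination, respectively".

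**The concern.** The derivation rule ties the last revaccination to a visit at which nobody is vaccinated. A programmer who follows the words about the last dose and one who follows the named visit obtain different end dates for the same subject. The gap between those dates depends on how late Visit 5 took place, so it varies from subject to subject.

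This matters because the analysed quantity is the largest value in the window. Adding days can add a new maximum but can never remove one. Under the Visit 5 reading, the reported percentage would cover a period longer than the one stated in the endpoint, and part of any decline presented as occurring within 3 months of vaccination would have occurred later. Allograft function is a named safety interest in a study without a control group, so the percentage needs a single definition.

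**Working it through.** **Inputs**

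- One month is 30 days, as in protocol Table 4, where 12 months equal 360 days. Three months are therefore 90 days.
- Visit 3 (dose 1) to Visit 4 (dose 2), *d*: 30 to 60 days, optimally 30 (Table 4); 30 to 182 days in special circumstances (Table 8).
- Visit 4 to Visit 5, *v*: 30 to 48 days (Table 4, repeated in the Table 8 note as "Optimally 30 – 48 days after Visit 4 (Table 4"); 30 to 90 days in special circumstances (Table 8).
- The SAP does not state when the post-baseline window opens. I take dose 1 at Visit 3, because protocol 8.1.9 collects from there.

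**Step 1. Can the stated anchor be reproduced?** Dose 1 is at Month 24 and dose 2 one month later, so the last dose is at 24 + 1 = Month 25, Visit 4. The SAP label of Visit 5 (Month 26) is not reproduced. Giving dose 2 at the latest standard day, 60 days after dose 1, moves it to about calendar Month 26. That visit is still Visit 4, and Visit 5 follows at least 30 days later. No permitted schedule makes Visit 5 a dosing visit.

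**Step 2. End of the window, counted from dose 2.**

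- Anchor on the last dose: 90 days, nominally Month 25 + 3 = Month 28.
- Anchor on Visit 5: *v* + 90, nominally Month 26 + 3 = Month 29.
  - Table 4: 30 + 90 = 120 to 48 + 90 = 138 days.
  - Table 8 limit: 90 + 90 = 180 days.

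**Step 3. Relative lengthening of the whole post-baseline window, counted from dose 1.** The dose anchor gives *d* + 90 days and the Visit 5 anchor *d* + *v* + 90, so the excess is *v* / (*d* + 90).

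| Schedule | *d* | *v* | Dose anchor | Visit 5 anchor | Excess |
|---|---|---|---|---|---|
| Optimal | 30 | 30 | 120 | 150 | 25% |
| Table 4, smallest | 60 | 30 | 150 | 180 | 20% |
| Table 4, largest | 30 | 48 | 120 | 168 | 40% |
| Table 8, largest | 30 | 90 | 120 | 210 | 75% |

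**Step 4. Direction of the effect.** With baseline fixed, the maximum over a longer set of values is at least the maximum over the shorter set. The count at 1.2-fold or more can stay the same or rise; it cannot fall.

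**Step 5. One-dose subjects.** Protocol 7.7 allows the second dose to be withheld, for instance after a biopsy-proven rejection between Visits 3 and 4. The last dose is then at Visit 3 and the endpoint closes at about 24 + 3 = Month 27. A Visit 5 anchor gives about Month 29 if that visit takes place and is undefined if it does not.

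**Step 6. Is the longer window declared?** SAP 4.8 lists the changes to protocol-defined analyses and does not mention this window. The version history says that the baseline and post-baseline definitions entered 6.2.3 in version 2.0 to clarify the handling of multiple measurements, so this is the text that is meant to settle the derivation.

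**The case against.** The strongest reply is that the sentence also says last revaccination. Programmed from the recorded dose date, it matches the endpoint exactly. That stands: the text is ambiguous, and a reader should not infer that the analysis certainly departs from the endpoint. However, protocol 8.1.9 first collects through Visit 5 and only then for a further 3 months to obtain additional values, so Visit 5 is the more natural working anchor, and nothing in the SAP excludes it.

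Three stronger readings should be resisted.

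- *The window is 33% to 100% longer.* Those figures (30/90 and 90/90) count only the tail after dose 2. The maximum is taken over the whole period after dose 1, so Step 3 is the relevant comparison.
- *Decline 4 to 6 months after the last dose is swept in.* Under Table 4 the added period ends at 120 to 138 days, which is 4 to 4.6 months. Six months arises only at the Table 8 limit.
- *The flag rate is inflated by a known amount.* It is not known. The documents give no creatinine variability, and protocol 8.1.9 leaves the timing of tests to the sites. For a stable graft with assumed monthly lognormal values and a mean of three baseline values, moving from 4 to 5 post-baseline values changes the simulated chance of a 1.2-fold flag from 0.28% to 0.35% at a within-subject CV of 5%, from 8.2% to 10.0% at 8%, and from 17.8% to 21.1% at 10%. At 10%, the 1.5-fold rate is about 0.1% either way. Even the largest of these shifts is about two subjects in the 68 enrolled (0.033 × 68 = 2.2).

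Two further points stand. The SAP 4.5.3.1 listing shows every creatinine value with its fold increase and the revaccination dates, so late values can be identified. And the longer reading cannot hide a decline within 3 months of the last dose.

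**Conclusion.** The contradiction is certain. The endpoint closes 3 months after the last dose, that dose is at Visit 4, and the derivation rule names Visit 5. Whether the analysed window actually differs depends on which anchor is programmed. If it is Visit 5, the window closes 120 to 138 days after dose 2 under Table 4 and up to 180 days under Table 8, against about 90. These figures rest on 30-day months and, for the percentages, on a window that opens at dose 1. The count of subjects flagged can then only be equal or higher, by an amount that the documents do not allow one to compute.

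The point is confined to one descriptive secondary safety endpoint. No primary analysis, hypothesis test or sample size depends on it. It should still be corrected, because the wording sits in the operative rule for the flag.

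**What to change.** In SAP 6.2.3, replace the Visit 5 (Month 26) label with the date of the subject's last administered revaccination dose: normally Visit 4, or Visit 3 if only one dose was given. State when the post-baseline window opens, close it for the flag 3 months after that date, and keep later values in the listing.

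The collection period in protocol 8.1.9 can stay as it is; only its visit label needs to be reconciled with the dosing schedule. Collecting for longer than the analysis window does no harm.

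If the longer window is intended, say so in SAP 4.8, align the endpoint wording in SAP 1.1 and protocol Table 5, and define the rule for subjects without a Visit 5.

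For the preferred option the cost is one sentence and one derivation in the SAP, plus the label correction in the protocol. No new data are needed, and values already recorded beyond the window remain visible.

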6.3. Criteria for temporary delay for revaccination

Revaccination may be postponed within the allowed time interval (see [Table 4](#)) until transient circumstances cited below have been resolved:

- Acute disease and/or fever at the time of revaccination. Fever is defined as temperature $\geq 38.0^{\circ}\text{C}$. The preferred route for measuring temperature in this study is oral. Subjects with a minor illness (such as mild diarrhea, mild upper respiratory infection) without fever may, be revaccinated at the discretion of the investigator.
- Allograft instability [greater than 20% variability between last two clinically obtained creatinine measurements or calculated glomerular Filtration Rates (GFR)].
- Any condition which, in the judgment of the investigator, would make IM injection unsafe.

CONFIDENTIAL212340 (ZOSTER-073 EXT:041 Y4-10)
Protocol Amendment 1 Final

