4.3.2.1. Long-term follow-up phase

The results for the analysis of safety in the long-term follow-up phase will be tabulated as follows:

- Number and percentage of subjects reporting at least one SAE related to primary vaccination in study ZOSTER-041 classified by Medical Dictionary for Regulatory Activities (MedDRA) Primary System Organ Class (SOC) and Preferred Term (PT) from the day after

ZOSTER-041 last study visit (Month 13) to ZOSTER-073 pre-revaccination (Visit 3 Month 24) will be tabulated with exact 95% CI.

- Number and percentage of subjects with at least one suspected or biopsy-proven allograft rejection from ZOSTER-041 last visit (Month 13) to ZOSTER-073 Day 1 will be tabulated with exact 95% CI.
- Number and percentage of subjects with at least one biopsy-proven allograft rejection from ZOSTER-073 Day 1 to ZOSTER-073 pre-revaccination (Visit 3 Month 24) will be tabulated with exact 95% CI.
- Number and percentage of subjects with suspected or confirmed HZ cases from ZOSTER-041 last visit (Month 13) to study ZOSTER-073 Day 1 will be tabulated with exact 95% CI.
- Number and percentage of subjects with confirmed HZ cases from ZOSTER-073 Day 1 through ZOSTER-073 study Month 24 will be tabulated with exact 95% CI.
- Listing of subjects with history of suspected allograft rejection or history of biopsy-proven allograft rejections from ZOSTER-041 last study visit to ZOSTER-073 Day 1 will be provided.
- Listing of subjects with biopsy-proven allograft rejections from ZOSTER-073 Day 1 onward will be provided.
- Listing of subjects with a suspected or confirmed HZ episode from ZOSTER-041 last study visit to ZOSTER-073 Day 1 will be provided.
- Listing of subjects with a confirmed HZ episode from ZOSTER-073 Day 1 onward will be provided.
- Number of subjects with declining allograft function (following HZ and allograft rejection episodes), as determined by fold change from baseline serum creatinine measurements, for the time period from study ZOSTER-041 last visit (Month 13) to study ZOSTER-073 Visit 3 (Month 24). This serum creatinine fold change from baseline will be summarized descriptively. A list of subjects with an increase in serum creatinine will also be presented. Allograft dysfunction is defined as having a fold increase in serum creatinine of 1.2 or greater from the reference timepoint.

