4.5.3. Additional Safety Assessments

4.5.3.1. Laboratory Data

Allograft dysfunction will be assessed through serum creatinine measurements. The number and percentage with an increase from baseline (≥ 1.2 , ≥ 1.5 , ≥ 1.75 , ≥ 2 fold) in serum creatinine related to allograft rejection episodes, revaccination, and HZ episodes. will be tabulated based on whether the episode fell in the time frames outlined in Section [4.3.2.1](#) and Section [4.3.2.2](#)

See Section 6.2.3 for definitions of baseline and handling post-baseline measurements related to rejection episodes, revaccination, and HZ episodes.

A listing of raw serum creatinine measurements and their corresponding fold increase from baseline will be provided for each individual subject. Changes from baseline and percent changes from baseline will also be included for each subject, along with their primary and revaccination dates, if applicable.

Replacement kidney since ZOSTER-041 will also be listed.

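### Allograft dysfunction after revaccination is read from the highest of an uncapped number of creatinine values against a baseline mean at 1.2-fold, so the rate is biased upward, rises with test frequency and can include stable grafts

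*SAP*

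**What the plan says.** Allograft dysfunction following revaccination, assessed through serum creatinine, is a secondary safety endpoint (Protocol section 4; SAP 1.1).

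- **Baseline.** SAP 6.2.3: "The average of measurements taken 3 months prior to first revaccination, Visit 3 (Month 24), will be used as pre-vaccination baseline". If there are too few values, sites "then go back to 4 or 5 months prior to revaccination to have a minimum of 3 measurements". The SAP does not say what happens if three still cannot be found.
- **Post-revaccination value.** SAP 6.2.3 uses "The maximum of measurements taken up to 3 months after last revaccination, Visit 5 (Month 26"). It sets a lower limit of three on the number of values and no upper limit.
- **Test frequency.** Protocol 8.1.9 relies on each site's surveillance practice and "will not mandate the type or timing of tests to participating study sites".
- **Definition.** SAP 4.3.2.1, repeated in 4.3.2.2: "Allograft dysfunction is defined as having a fold increase in serum creatinine of 1.2 or greater from the reference timepoint". No repeat value is required.
- **Display.** SAP 4.5.3.1 tabulates increases of "≥ 1.2 , ≥ 1.5 , ≥ 1.75 , ≥ 2 fold" and lists each subject's raw values with fold, absolute and percent changes.
- **Comparison.** The study is uncontrolled. SAP 4.5 mentions comparing non-revaccinated with revaccinated subjects after Visit 3.

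SAP 6.2.3 attaches Visit 5 (Month 26) to the last revaccination, but the second dose is given at Visit 4 (Month 25). The end of the window is therefore unclear by about a month, and these passages need to be reconciled.

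**The concern.** If a graft is stable, the highest of several later values will still tend to lie above the average of the earlier ones. The expected ratio exceeds 1 with no change in function, and each extra test gives another chance to cross 1.2. Two equally stable subjects at sites with different surveillance schedules have different chances of being labelled dysfunctional.

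This matters because the label is a safety finding. Protocol 3.3.1 names allograft rejection as a theoretical concern with adjuvanted vaccines in this population, so the rate will be read closely. A reader has nothing to calibrate it against. There is no control group, and the non-revaccinated subjects are measured differently: SAP 6.2.3 takes their baseline from before primary vaccination and their maximum from Visit 3 to study end, about 25 months (Month 24 to Month 49). Both the reference and the window differ from those used for revaccinated subjects.

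**Working it through.** The plan states no expected or background rate of dysfunction, so there is no figure of its own to reproduce.

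**Inputs from the documents:** threshold 1.2; baseline is a mean of an intended three or more values; post value is a maximum of three or more values; 68 subjects enrolled (SAP Table 1). The number revaccinated is not given, so 68 is an upper bound.

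**Assumed inputs:** exactly 3 baseline values; 3, 5 or 8 post values; CV from 5% to 10%; independent errors; no true change.

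**Where the CV might lie.** The only related figure is the delay criterion in Protocol 6.3: "Allograft instability [greater than 20% variability between last two clinically obtained creatinine measurements". If that 20% is read as a 95% limit for the difference between two values, which is an assumption and not something the protocol says, then CV = ln(1.2)/(1.96 × √2) = 6.6% on the log scale, or 0.20/(1.96 × √2) = 7.2% on the percent scale.

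**Model.** Each value is the subject's true level times exp(σZ), with Z standard normal and σ = √ln(1 + CV²). The true level cancels in the ratio. With B the mean of three such baseline multipliers and m post values:

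P(flag) = P(max post / B ≥ 1.2) = 1 − E[Φ(ln(1.2·B)/σ)^m]

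**Check by hand with m = 1, CV 8%.** σ = √ln(1.0064) = 0.0799. The standard deviation of the log ratio is about 0.0799 × √(1 + 1/3) = 0.0922. Then ln(1.2)/0.0922 = 0.1823/0.0922 = 1.98, an upper tail of about 2.4%. Simulation gives 2.3%.

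**Stable grafts flagged, by simulation:**

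| CV | 3 post values | 5 post values | 8 post values |
|---|---|---|---|
| 5% | 0.2% | 0.4% | 0.6% |
| 6.6% | 2.3% | 3.7% | 5.6% |
| 7.2% | 3.8% | 6.0% | 9.1% |
| 8% | 6.4% | 9.9% | 14.6% |
| 10% | 14.1% | 21.2% | 29.4% |

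The effect of the maximum alone shows at CV 8%: 2.3% with one post value, 14.6% with eight.

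**In subjects**, with 5 post values and at most 68 people: 68 × 0.004 = 0.3 at CV 5%; 68 × 0.037 = 2.5 to 68 × 0.060 = 4.1 at CV 6.6 to 7.2%; 68 × 0.099 = 6.7 at CV 8%; 68 × 0.212 = 14.4 at CV 10%.

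**What the existing higher rows do.** At 1.5-fold, no more than about 0.2% of stable grafts are flagged up to CV 10%.

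**Two consecutive post values at 1.2-fold or more.** The stable-graft rate falls to between 0 and 3.7% over the CV 5 to 10% range. If successive values have a lag-1 correlation of 0.5, it can reach 9.7% (CV 10%, 8 post values). With 5 post values and CV 8 to 10%, this rule still detects 86 to 91% of sustained 1.3-fold rises and over 99% of sustained 1.5-fold rises.

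**Mean post over mean baseline.** At CV 8% with 5 post values, a true 1.5-fold rise confined to the last two values is flagged 50% of the time, against 98% for two consecutive values and 100% for the maximum.

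**The case against.** The strongest reply is that a maximum at a low threshold is a legitimate choice for safety. It errs towards over-reporting harm, the study is descriptive, biopsy-proven rejection is reported separately, and the table already has rows at 1.5-fold and above that are almost free of noise up to CV 10%. The listing shows every value, so a reader can count tests and look for confirmation. All of this stands. It argues for keeping the maximum and its definition, not for leaving the 1.2-fold row without context: that row carries the dysfunction label, and a descriptive rate still has to mean what its label says.

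A reader might infer three stronger things, and the documents do not support them.

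- **That many stable grafts will be flagged.** This rests on a CV that neither document gives. At CV 5% the expected number is below one subject; the share is large only towards CV 10%.
- **That Protocol 6.3 concedes 20% to be ordinary variation.** It does not. It treats more than 20% between two values as instability and a reason to postpone a dose, which fits a sensitive 1.2-fold cut-off equally well.
- **That the 1.2-fold definition should be replaced.** Each alternative loses sensitivity. At CV 8% with 5 post values, a true 1.3-fold rise on the last value alone is flagged 81% of the time by the maximum but only 2.5% by two consecutive values.

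**Conclusion.** The point holds as a limited one that is cheap to put right. The direction of the bias follows from the rule itself at any CV: the 1.2-fold rate is pushed upward, it rises with a test count that sites determine, and no comparable background rate is planned. The size is uncertain. Over 3 to 8 post values, the share of stable grafts flagged runs from 0.2 to 0.6% at CV 5% up to 14 to 29% at CV 10%, with 2 to 9% at the CV obtained by reading the protocol's 20% figure as a 95% limit. These figures rest on independent lognormal errors, three baseline values and no drift; correlated errors or a slow true decline would change them. The higher-multiple rows and the listing contain much of the harm, but they do not tell a reader how much of the 1.2-fold row could be noise.

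**What to change.** Leave the maximum-based 1.2-fold definition and the existing rows as they are. In the SAP 4.5.3.1 table for revaccination, add one supplementary row: subjects with a rise of 1.2-fold or more over baseline on two consecutive post-revaccination measurements. Alongside it, show the number of post-revaccination measurements per subject. Do not use mean post over mean baseline as the alternative, because it dilutes a late rise.

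The cost is one row and one count from creatinine values that are already collected and listed. The downside is that the confirmed row misses a single transient rise and a rise that begins at the last measurement in the window. Both remain visible in the maximum row and in the listing.
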